9.7.5 Secondary Endpoint Analysis

The main secondary endpoint variable will be the change in HAQ DI at 12 weeks after the initiation of adalimumab.

The objective of endpoint analysis will be to demonstrate that treatment with adalimumab improves functioning as measured by HAQ DI in subjects with RA compared to baseline.

The main secondary analysis will be summarized as the mean and 95% confidence interval and will be tested with a paired t-test without adjusting for baseline disease severity. For sensitivity analysis, the mean change in HAQ DI at Week 12 will be analyzed using ANOVA adjusting for baseline disease severity.

Other secondary analyses include:

- Change in other patient reported outcomes (SF-36 domain scales, EQ-5D Index, WPAI total lost productivity) at weeks 12 and 24 after the initiation of adalimumab, in those patients continuing on adalimumab (as observed population). These changes will be summarized as the means and 95% confidence intervals and will be tested with paired t-tests.
- Number and percent of patients achieving a clinically meaningful improvement on the HAQ DI, as defined by a -0.22 point improvement or greater, at weeks 12 and 24 after the initiation of adalimumab, in those patients continuing on adalimumab (as observed population).

9.7.6 Exploratory Endpoint Analysis

Additional analyses include:

- Change in HAQ DI score at 24 weeks after the initiation of adalimumab, in those patients continuing on adalimumab (as observed population), compared with those patients not continuing on adalimumab (withdrawal population). The mean changes in these two groups will be compared using an independent t-test.
- Healthcare resource utilization will be described using number and percentage within each category (number of consultations, number of procedures received, number of surgeries, number of hospitalizations and length of stay, number of concomitant medications)
- Change in patient satisfaction questions at weeks 12 and 24 after the initiation of adalimumab, in those patients continuing on adalimumab (as observed population). These changes will be summarized as number and percentage of each response and compared with Kruskal–Wallis test. Satisfaction will also be dichotomized and analyzed over time with Cochrane-Armitage test for trends.
- Patient's impression of change at weeks 12 and 24 after the initiation of adalimumab, in those patients continuing on adalimumab (as observed population). These changes will be summarized as number and percentage of each response and compared with Kruskal–Wallis test.
- Associations between disease severity and PROs
- Associations between change in disease severity and change in PROs

9.7.7 Safety Analysis

Adverse events occurring while participants are on adalimumab will be coded using Common Terminology Criteria for Adverse Events (CTCAE) classification individually listed by indication groups. The incidences and percentages of individuals experiencing AEs and SAEs within each indication will be summarized by System Organ Class (SOC) with further summaries by severity and relatedness (causality) categories. Adverse events leading to discontinuation and concomitant medications will also be listed and summarized.

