9.0 Research Methods

9.1 Study Design

This study is designed as a prospective, observational study to assess the effect of adalimumab on health-related QoL and work productivity in patients with RA in Taiwan in clinical practice.

Note: This study is non-interventional and the subjects/investigators will follow the current clinical practice in each site and also the routine clinical follow up as determine by the treating physician.

This study is non-interventional. Patient therapy is not decided by the study protocol but falls within current medical practice, and the prescription of adalimumab is clearly separated from the decision to include the patient in this study. The subjects/investigator will follow the current clinical practice in each site and also the routine clinical follow up as determine by the treating physician.

RA patients will be recruited from within the clinical settings of each rheumatologist participating in the study. Approximately 100 patients diagnosed with RA that meet the inclusion and exclusion criteria will be enrolled at approximately 7 sites in Taiwan.

To assess health and disability outcomes, the HAQ DI at baseline, Week 12 and Week 24 after treatment initiation with adalimumab will be collected. In addition, other PROs of work activity and well-being, including the WPAI, EQ-5D, and SF-36, will also be collected. All above instruments have been validated for the Chinese version.

The HCRU will also be collected. This includes surgical procedures, hospitalizations, bed days in hospital, physician consultations etc. Costs will be assigned based on the HCRU using standardized costs for each participating centers.

The patients identified by the recruiting investigators based on the study selection criteria will be collected data as observed on QoL, functioning, work productivity,

treatment satisfaction, impression of change and HCRU. Data will be captured at baseline (D0), Week 12 and Week 24.

Subjects may discontinue adalimumab treatment at any time during study participation. Subjects that end study participation early will have a Termination Visit, which may be a routine follow-up visit at investigator's clinic. All subjects will have a data recorded approximately 70 days after the Week 24 dosing or after the last administration of adalimumab to obtain information on any new or ongoing AEs.

Primary Endpoint Analysis

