- Associations between change in disease severity and change in PROs

Observation period

- Observation of safety till 70 days after the Week 24 dosing or after the last dose of adalimumab
- Observation of pregnancy till 150 days after the Week 24 dosing or after the last dose of adalimumab

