9.7 Data Analysis

9.7.1 Statistical and Analytic plans

A statistical analysis plan (SAP) will be developed describing the specific analysis that will be performed including, and in addition to, the analysis described here. All analysis will be performed in accordance with the approved analysis plan. The following provides an overview of some of the analysis.

The scoring of the PRO questionnaires will be done in accordance to the developers' recommendations.

A separate statistical analysis plan will be developed describing the specific analysis that will be performed including and in addition to the analysis described here.

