11.1.4 Adverse Event Collection Period

Adverse events will be reported to AbbVie from the time the physician obtains the patient's authorization to use and disclose information (or the patient's informed consent) until 70 days following the intake of the last dose of physician-prescribed treatment will be collected, whether solicited or spontaneously reported by the subject. In addition, serious adverse events will be collected from the time the subject signed the study-specific informed consent. Adverse event information will be collected and recorded on the appropriate eCRFs.

Subjects will be contacted approximately 70 days following the intake of the last dose of physician-prescribed treatment for an assessment of any new or ongoing AEs.

All SAEs, as defined by AbbVie, reported during the 70-day follow-up phone call must be captured in the clinical database.

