6. LIST OF TABLES AND FIGURES IN EXCEL WORKBOOK

Results of the analysis for this study as outlined above will be summarized using MS Excel tables and will be presented as follows:

Excel Tables / Figures	Description
1	Demographic Characteristics at Baseline
2	Clinical Characteristics at Baseline
3.1	Change in HAQ DI at Weeks 12 and 24 after Initiation of Adalimumab
3.2	Change in HAQ DI at Weeks 24 after Initiation of Adalimumab - Observed VS Withdrawal Population
4	Change in SF-36 Domain Scales at Weeks 12 and 24 after Initiation of Adalimumab
5	Change in EQ-5D-3L Index at Weeks 12 and 24 after Initiation of Adalimumab
6	Change in WPAI at Weeks 12 and 24 after Initiation of Adalimumab
7	Change in Patient Satisfaction Questions at Weeks 12 and 24 after Initiation of Adalimumab
8	Patients' Global Impression of Change at Weeks 12 and 24 after Initiation of Adalimumab
9	Post-index Healthcare Resource Utilization - RA Related
10.1	Associations between Disease Severity and PROs
10.2	Associations between Change in Disease Severity and Change in PROs
11	GLM - Modifying Effects on Changes in PROs

Please see the document, "AbbVie_ROCKI_Tableshell_V0.2_15Jan2018_Taiwan.xlsx" for the full set of table shells.

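### Protocol 9.7.7 codes adverse events only while patients are on adalimumab although collection runs 70 days longer, and the SAP omits the safety analysis altogether

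*Protocol*

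**What the plan says.** Protocol 9.7.7 sets the scope of the safety analysis in its first sentence: "Adverse events occurring while participants are on adalimumab will be coded using Common Terminology Criteria for Adverse Events (CTCAE) classification". The next sentence gives the summary: "The incidences and percentages of individuals experiencing AEs and SAEs within each indication will be summarized by System Organ Class (SOC"), with breakdowns by severity and relatedness. A last sentence adds events leading to discontinuation. The section does not define being on adalimumab and gives no post-dose window.

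Collection is wider. Under Protocol 11.1.4, events are reported from consent, "until 70 days following the intake of the last dose of physician-prescribed treatment will be collected, whether solicited or spontaneously reported by the subject". Protocol 9.1 adds "All subjects will have a data recorded approximately 70 days after the Week 24 dosing or after the last administration of adalimumab" and sets the observation period as "Observation of safety till 70 days after the Week 24 dosing or after the last dose of adalimumab"; Protocol 9.2.6 repeats the 70-day contact.

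On the role of the SAP, Protocol 9.7.1 states: "All analysis will be performed in accordance with the approved analysis plan". It also says that the SAP will contain the protocol's analyses and more. SAP section 6 opens with "Results of the analysis for this study as outlined above will be summarized using MS Excel tables" and lists Tables 1 to 11. None of them concerns adverse events.

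**The concern.** Two gaps lie one on top of the other.

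- **Window.** The protocol asks sites to gather events for 70 days after treatment ends, then states an analysis rule that stops when treatment stops. Followed as written, the rule leaves collected events uncoded. The proportion of patients with at least one event can then only equal or fall below the proportion over the full collection window. The omitted time includes the weeks after a patient stops because of toxicity.
- **SAP.** The governing analysis document carries no safety output, on drug or off. The window, the population and the layout of the safety tables would therefore be settled after the data are in hand.

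The protocol gives its own reason to care. Section 8.1 says safety information from this study is meant to help confirm the known profile and to pick up unknown, rare and long-latency reactions. An analysis that ends with the last dose works against the long-latency part of that aim.

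**Working it through.** The plan states no figure on this point, so there is none to reproduce. The check is a comparison of passages, followed by a calculation for scale.

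**1. The windows side by side**

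| Source | Start | End |
|---|---|---|
| Protocol 11.1.4, collection | Consent | 70 days after last dose |
| Protocol 9.1 and 9.2.6, safety follow-up | – | About 70 days after Week 24 dosing or last dose |
| Protocol 9.7.7, coding and listing | On adalimumab | On adalimumab; end not defined |
| Protocol 12.6, after drop-out | – | Nothing further collected, apart from the reason and any adverse event that caused the stop |
| SAP | No analysis | No analysis |

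On a plain reading, 9.7.7 omits events between consent and first dose, and events after the last dose.

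**2. Does the limit reach the incidence summaries?** The incidence sentence does not repeat it. But a summary by System Organ Class needs events that have been coded, and the only coding 9.7.7 provides for is of on-drug events. The limit therefore carries through in effect. Usage elsewhere supports the narrow meaning: 9.7.6 sets patients continuing on the drug against the withdrawal population, and 9.7.9 sets discontinuation against remaining on the drug.

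**3. Tracing 9.7.7 into the SAP.** The SAP takes over the protocol's primary, secondary, exploratory, effect-modifier and missing-data plans (SAP 2.1–2.3, 3.5.5, 5.3–5.5). It has no safety objective, no safety section and no safety table. Adverse events appear as a data source (3.3.1) and safety as a purpose of source review (3.3.4). The abbreviations CTCAE and SOC are defined in section 7 but support no analysis. This looks like an omission rather than a decision.

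**4. Scale.** Inputs from the documents: about 100 patients; 24 weeks = 168 days on drug for a completer; 70 days of follow-up; drop-out 10% (Protocol 9.5) or 13% (SAP 4). Assumptions not in the documents: all drop-outs stop the drug, at a day between 14 and 154; everyone is followed for the full 70 days; time is counted from first dose.

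One patient stopping at Week 24: 70 / (168 + 70) = 70 / 238 = 29.4% of follow-up is off drug.

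For 100 patients with drop-out fraction d and drop-out day t:

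- Total person-days = 100(1 − d) × 168 + 100d × t + 100 × 70
- Off-drug share if everyone stops by Week 24 = 7,000 / total
- Off-drug share if only drop-outs stop = (100d × 70) / total

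| d | t | Total | Everyone stops | Only drop-outs stop |
|---|---|---|---|---|
| 10% | 14 | 15,120 + 140 + 7,000 = 22,260 | 31.4% | 700 / 22,260 = 3.1% |
| 10% | 154 | 15,120 + 1,540 + 7,000 = 23,660 | 29.6% | 700 / 23,660 = 3.0% |
| 13% | 14 | 14,616 + 182 + 7,000 = 21,798 | 32.1% | 910 / 21,798 = 4.2% |
| 13% | 154 | 14,616 + 2,002 + 7,000 = 23,618 | 29.6% | 910 / 23,618 = 3.9% |

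The documents do not say how many completers stay on treatment under routine care, so under these assumptions the share lies somewhere between about 3% and 32%.

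**The case against.** The strongest replies, and what stands of each:

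- **Post-dose events are not lost.** A reader might infer that they would go unreported. The documents do not support that. Protocol 11.1.5 has serious events notified within 24 hours with no on-drug limit, 11.1.4 puts serious events from the 70-day call into the clinical database, and event information goes onto the eCRF. This stands in full. What is missing is planned coding and summary.
- **The limit sits in one sentence only, and being on adalimumab is undefined.** True as text, so some latitude remains. It does not rescue the plan: the summaries depend on coding, and an undefined safety window needs fixing in any case.
- **A safety analysis is planned, in the protocol.** A reader might infer that none exists anywhere. In fact 9.7.7 remains prespecified, and 9.7.1 intended the SAP to include it. The fault is a mismatch between protocol and SAP. That limits the charge but leaves the SAP, the document to be followed, without a safety table.
- **Safety is not a stated objective, and non-serious events are not actively solicited** (Protocol 11.1.1). This lowers the weight of non-serious counts. It does not touch serious events, which are actively solicited.
- **Post-dose data may not exist for those who stop.** Protocol 12.6 counts being switched off adalimumab as drop-out and then ends collection, against 9.1, 9.2.6 and 11.1.4. This is a real contradiction, and it must be resolved before any window can work.

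**Conclusion.** The point holds in this form: a stated analysis restriction conflicts with the protocol's own collection window, and the SAP omits the 9.7.7 analyses although it governs all analysis. Events outside treatment have no clearly planned coding or summary, and on-drug events have no SAP table either. The restriction can only leave incidence unchanged or lower it.

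The size cannot be given as a number of missed events. Off-drug time is about 3–4% of person-days if only drop-outs stop and about 30% (29.6–32.1%) if everyone stops by Week 24, under the assumptions listed with the calculation. Two stronger inferences should be resisted:

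- The 29.4% for a patient stopping at Week 24 is a share of calendar time, not of events. For a completer who continues, the 70 days after the Week 24 dosing are on drug.
- The assumed drop-out of 10–13 per 100 is not a floor for patients affected. Protocol 12.6 also counts patients who decline further participation, who may remain on the drug, and patients lost to contact, who can supply no post-dose data.

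This should be corrected, but it does not bear on the primary HAQ DI analysis.

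**What to change.** 1. **Protocol 9.7.7.** Replace the on-drug restriction with the collection window of 11.1.4: consent to 70 days after the last dose. For patients who continue treatment, use the Week 24 dosing anchor of 9.1, since their last dose has no fixed date and may fall after the end of data collection. Flag events before first dose and after last dose so that on-drug results can still be shown separately.
2. **SAP.** Add a safety section and tables for adverse events, serious adverse events and adverse events leading to discontinuation, by System Organ Class, severity and relatedness, in all patients with at least one dose (the Protocol 9.7.2 population). Add these tables to the section 6 list.
3. **Protocol 12.6.** Reconcile the end of data collection at drop-out, which includes being switched off adalimumab, with the 70-day follow-up in 9.1, 9.2.6 and 11.1.4.

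The cost is one wording change, a short SAP section with about three standard tables, and one reconciliation. No assessment is needed beyond the follow-up that 9.1, 9.2.6 and 11.1.4 already require.

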9.7.8 Additional Analysis

Additional analysis will explore the potential modifying effects of baseline measures on the changes in primary and secondary efficacy outcomes. These measures will include age, gender, baseline severity, and other diagnoses/co-morbidities. The analysis will specifically test for differential changes across the subgroups defined by the potential modifiers using general linear models.

9.7.9 Missing Data

Efficacy measures are not assessed after a participant discontinues adalimumab. The exception to this will be the analysis of proportion of patients at 24 weeks who remain on adalimumab. Item level data on the PROs will be imputed according to the developers' recommendations. There will be no other imputation for missing data.

9.7.10 Interim Analysis

There is no interim analysis planned for this study.

9.8 Quality Control

9.8.1 Ethics and Quality

Prior to any study-related data being collected, informed consent form will be reviewed, signed and dated by the patient and the person who administered the informed consent. A copy of the signed informed consent will be given to the patient and the original will be placed in the patient's medical record.

9.8.2 Quality Assurance

Prior to the initiation of the study, physician and site personnel will be trained on the study. Training will include a detailed discussion of the protocol, performance of study procedures, and completion of the CRFs and paper questionnaires.

All sites will be monitored during the course of study participation. One hundred percent (100%) source document review for safety will be performed.

All clinical data will be documented via the CRF. Study coordinators at each site will check the paper CRFs completed by the physicians and questionnaires completed by patients (e.g., all questions were answered). Data entry will be conducted by IMS. After entry of the data, computer logic checks will be run to check for inconsistent data. Any necessary corrections will be made to the database and documented via addenda, queries, and source data clarification forms.

Steps to be taken to ensure the accuracy and reliability of data include the selection of qualified investigators and appropriate study centers, review of protocol procedures with the investigator and associated personnel before the study and periodic monitoring visits by the sponsor. Written instructions will be provided for administration and collection of study questionnaires.

Guidelines for CRF completion will be provided and reviewed with study personnel before the start of the study. The sponsor will review CRFs and patient questionnaires for accuracy and completeness after transmission to the sponsor; any discrepancies will be resolved with the investigator or designee, as appropriate. After upload of the data into the clinical study database they will be verified for accuracy and consistency with the data sources.

Protocol Deviation

For the purposes of this protocol, reportable deviations are defined as:

- Subject entered into the study even though she/he did not satisfy entry criteria
- Subject who developed withdrawal criteria during the study and was not withdrawn
- Subject who received excluded or prohibited concomitant treatment

9.9 Limitations of the Research Methods

The study is to be performed as a non-interventional study. Unlike clinical studies, obtainable data are limited and there is a possibility of missing data.

9.10 Other Aspects

9.10.1 Note To File

The Principal Investigator or designee will be responsible for documenting study relevant information and occurrences that affects the course of the study. The information and occurrences are not protocol deviations but will be documented in a note to file and will be communicated to the sponsor.

9.10.2 Training Log

All designated study personnel must be trained on the study protocol and procedures. Training and retraining are documented on the Training Log.

9.10.3 Visitor Log

All Sponsor or other related individuals who visit the study site must sign the Visitor Log.

9.10.4 Responsibilities of the Principal Investigator

The Principal Investigator is responsible for oversight of enrolment, the patient consent process, study related procedures, compliance with the protocol, all institutional, state and local guidelines.

It is the responsibility of the Principal Investigator to select, supervise, and delegate responsibility for study conduct to staff members. The Principal Investigator is responsible for determining the appropriate staff qualifications required for specific study-related tasks to be delegated. Study-related tasks delegated to staff members will be documented on the Site Signature and Delegation Log.

9.10.5 End of Trial

End of Trial is defined as last subject's last visit (LPLV).

10.0 Protection of Human Subjects

This study must be conducted in compliance with the recommendations of the Declaration of Helsinki, 2008 (World Medical Association). In addition, this study will adhere to all general and local legal and regulatory requirements applicable to non-interventional studies.

Informed consent will be obtained from each subject before the subject can participate in the study. The contents and process of obtaining informed consent will be in accordance with all applicable regulatory requirements.

As required by applicable local regulations, the sponsor's Regulatory Affairs group will ensure all legal regulatory aspects are covered, and obtain approval of the appropriate regulatory bodies, prior to study initiation in regions where an approval is required.

This study is non-interventional and falls outside the scope of the EU Directive 2001/20/EC, the EU Directive 2005/28/EC and International Conference on Harmonization (ICH) Good Clinical Practice (GCP) guidelines.

This study complies with the EU Directive 95/46/EC of the European Parliament and of the Council of 24 October 1995 on the protection of individuals with regard to the processing of personal data and on the free movement of such data.

